**Remember to note any changes to the standard positions on the form above.**

### Weight measurement

#### Set up

- Scale is placed on uncarpeted floor / compressed carpet
- Scale is set on “lbs” not “kg”
- Client is not wear shoes or heavy jewelry or heavy clothing
- Ask client to use bathroom before measurement → **“The measurement we are about to take is more accurate if you use the bathroom before we measure you.”**

#### Measurement

- Ask client to step on the scale, feet positioned evenly on scale
- Client is still while weight is being determined, display will flash and then show the weight.
- Have client step off step off scale,
- Repeat 1-time, if different, repeat both measurements.**

Weight 1 
 
 				.		lb	
 
					.		lb	Weight 2 
 
 				.		lb	
 
					.		lb
				.		lb									
				.		lb									
notes: 
 
 weight greater than 400 lbs
 
 client needed support / help (specify)
 
															
 not needed. 
 
 				.		lb	
 
					.		lb	 not needed. 
 
 				.		lb	
 
					.		lb
				.		lb									
				.		lb									

#### Notes to data collector:

- Make certain that the scale is on “LB”
- Weigh yourself while setting up to ensure that the scale is accurate
- Do not press the on/off button on the scale before measuring. Just step onto the scale.
- If the client needs support during the weighing, provide the minimum support that is safe and note on the form above.

### Step 4: Medication List

- Double check that all medicines are listed
- Aspirin dose is noted
- Insulin is checked “yes” or “no”
- all doses and frequencies are listed
- For all medications – ask if it is taken as written on the bottle, if not, note on the form**

Brought Medications	 Yes	 No - schedule date/time for phone call:	
	 Yes-from list		
Takes a daily aspirin	 No	 Yes - note the mg per day:	_____ mg

Insulin Name	Mix (___/___)	Unit (s)	# times per day	Total dose (data entry only)	Notes

**Insulin** = state the full name

**Mix** = state the mix values (i.e. 70/30)

**# Times per Day** = state the number of times you take insulin in a day

**Dose/total dose** = (FOR DATA ENTRY ONLY) Use the # per day to determine the dose or doses of insulin the participant takes. Use this to calculate the total dose per day. (For example: # per day: 2, dose: 12 (am) & 25 (pm) → dose total: 37)

*Note any additional comments or concerns you might have about insulin:*

Medication Name	Combination Yes / No	Freq 1 # pills taken	Freq 2 # times / day	Dose	Total dose (data entry only)	Notes
	 Yes  No					
	 Yes  No					
	 Yes  No					
	 Yes  No					
	 Yes  No					
	 Yes  No					
	 Yes  No					
	 Yes  No					
	 Yes  No					
	 Yes  No					
	 Yes  No					
	 Yes  No					
	 Yes  No					
	 Yes  No					
	 Yes  No					
	 Yes  No					
	 Yes  No					
	 Yes  No					
	 Yes  No					

- **Medication name** = Write the full name
- **Combination** = If yes, remember to write the dose for both medications  
(Ex. Glucovance contains glyburide and metformin HCl → be sure to state the two doses i.e. 15/500)
- **Freq 1** = State the number pills taken for the medicine (ex. 2 pills in the AM, 3 pills in the PM)
- **Freq 2** = State the number of times the pills are each day (ex. 2 times a day)
- **Dose** = the dose of the pill. **Remember to write dose of both meds if a combination (ex: 15/500)**
- Total Dose = (FOR DATA ENTRY ONLY) use freq 1 and freq 2 to calculate (Ex. 1.5 mg = 1 pill, frequency = 2 pills are taken 3 times a day, dose = 3 mg & total dose: 9 mg)

Note any additional comments or concerns you might have about medication list

Additional pages needed ( \_\_\_\_\_ ) pages attached.

Report Card

- Complete report card and present to the client.
- Living Well personnel should provide the results of the biometric measurements and explain what the numbers mean. **Their role is not to provide medical advice. If participants have questions beyond the explanation of the values and the risks that may be associated with elevated values, participants should be instructed to talk to their health care providers.**
- Review the script on page 29-30 of the Biometric Protocol.

Next Steps

- Peer Advisor will call you in 1-2 weeks.
- Obtain preferences for times that peer should call.*

**Best Times to Call**

- |                                     |                               |                                |                              |
|-------------------------------------|-------------------------------|--------------------------------|------------------------------|
|  Morning    |  Mon  |  Thurs |  Sat |
|  Afternoons |  Tues |  Fri   |  Sun |
|  Evenings   |  Weds |                                |                              |

**If the participant is in the Living Well program:**

- Give participant Program packet.*
  - Please keep the DVD in a safe place. You will be able to keep the DVD at the end of the study, but it is very important for you to have for the study.
  - Also, please place the DVD player and program materials in a safe place. You will need these materials when your peer advisor calls you.
- Offer study phone to the participant*
  - Study phone are available for you to use for the length of the research study. Please only use this phone with your calls with your peer advisor. Please do not use the phone for personal calls. This phone will need to be returned to UAB at the end of the research study. Would you like to use a study phone?
    - Yes, client will like to use a research study phone.
    - No, client declines the use of a research study phone.
- Thank the client; another data collection will take place in 6 months. Show client where the phone numbers are to reach community coordinators and Birmingham staff.*

**If the participant is in the General Health Program:**

- Give participant Program packet.*
- Thank the client; another data collection will take place in 6 months. Show client where the phone numbers are to reach community coordinators and Birmingham staff.*

DVD Set Up

- Have client practice and set-up the DVD from the beginning.
- While cleaning-up and packing, have the client watch DVD 1.

[figure not shown]

# Health Report Card

# Report Card

There are some things you can do to reduce the health risk of diabetes.

These numbers can give you an idea of how you are doing.

*You may want to talk to your doctor about...*

## A1C (Average Sugar Control over the last 3 months)

- Great control** Less than 7
- Ok, not perfect** 7.0 ↔ 7.9
- Cause for concern** 8.0 ↔ 8.9
- Bigger cause for concern** > 9.0

## Blood Pressure

- Normal** Less than 120/80
- Our Goal** Less than 140/90
- High-talk to doctor** 140/90 or higher

## Cholesterol (LDL cholesterol or your "bad cholesterol")

- Okay** Less than 100
- High-talk to doctor** 100 or higher

## Weight

- Normal**  
*(excellent)*
- Overweight**  
*(may be concerning)*
- Obese**  
*(take action)*

## Appendix G

### **Participant Retention Postcards**

## General Health Education Program Video Fact

Living healthy can lower your risk of eye disease!  
Keep an eye on your health by eating fruits and  
vegetables, being active, and not smoking!

To find out more, please watch **Video 5: Eye Care** on the  
General Health Education Program DVD.

*Have questions?*

*Contact the UAB Living Well study team at:*

**[contact]**

**Did you know?**

**Keep in touch!**

**Just a reminder, your 6 month visit is coming up!  
We will be in contact to schedule this meeting soon.**

**Remember! Your 6 month visit is coming up soon!**  
*Got questions? Call us at [name]*

# Reminder!

Your **telephone appointment** has been scheduled for

*date:* \_\_\_\_\_

*time:* \_\_\_\_\_

We look forward to speaking you!

If you have questions, please call us using the numbers listed below.

We look forward to speaking with you!

If you have questions, please call us at: [contact]

*All Participants - Thanksgiving*

[figure not shown]
# *Happy Thanksgiving*

from the UAB Living Well Study Team

*Got questions? Call us at [name]*

# Retention Scripts

## General Health Program Participant Phone Call Script – Month 1

### ***Voicemail leave message 1 time only:***

Hello, my name is \_\_\_\_\_, I am calling from the University of Alabama at Birmingham about the Living Well program. At your convenience, please call us at [contact]. Thank you and have a nice day.

Hello \_\_\_\_\_, my name is \_\_\_\_\_ calling from the University of Alabama at Birmingham about the Living Well research program. How are you today?

May I please speak with \_\_\_\_\_?

- [If not speaking] Is \_\_\_\_\_ available?
- [If no] When may I call back to speak with \_\_\_\_\_? Thank you for your time.  
*[Document Date/Time to call back]* \_\_\_\_\_
- **[If yes continue when they come on the line]** Hello \_\_\_\_\_, my name is \_\_\_\_\_ calling from the University of Alabama at Birmingham about the Living Well study. How are you today?

### **I am calling today to welcome you to the Living Well General health research study and go over any questions you have about the study.**

- Have you watched any videos from the General Health DVD? Do you have any questions about any of the materials?
- May I answer any questions that you may have about the study?

### **I would like to verify your contact information. Is this your correct mailing address and telephone number?**

**Yes – great thank you!** *(move to next question)*

**No – obtain correct information and update spreadsheet.**

**We also have \_\_\_\_\_ (name) as a friend or family member who would know your whereabouts in case we have trouble contacting you. Is this still the correct phone number for \_\_\_\_\_ (name)?**

**Yes – go to close out**

**No – Can you give me another person who would know your whereabouts in case we have trouble contacting you? Please think of someone who would not mind if we called them for this information.**

### ***Close out:***

- ***Thank you again for your time today.*** A member of our team will be contacting you each month by mail or phone. If you would like to reach us before we talk again you can call us at the number listed on your DVD. If your phone number or address changes, or if you have any questions about the Living Well with Diabetes study, please call us at the same number. Thank you and have a wonderful day!

### General Health Program Participant Phone Call Script – Month 3

***Voicemail leave message 1 time only:***

Hello, my name is \_\_\_\_\_, I am calling from the University of Alabama at Birmingham about the Living Well program. At your convenience, please call us at [contact]. Thank you and have a nice day.

Hello \_\_\_\_\_, my name is \_\_\_\_\_ calling from the University of Alabama at Birmingham about the Living Well research program. How are you today?

May I please speak with \_\_\_\_\_?

- [If not speaking] Is \_\_\_\_\_ available?
- [If no] When may I call back to speak with \_\_\_\_\_? Thank you for your time.  
*[Document Date/Time to call back]* \_\_\_\_\_
- **[If yes continue when they come on the line]** Hello \_\_\_\_\_, my name is \_\_\_\_\_ calling from the University of Alabama at Birmingham about the Living Well study. How are you today?

**I am calling today to check in with you and answer go over any questions you have about the study.**

- Have you watched any videos from the General Health DVD? Do you have any questions about any of the materials?
- May I answer any questions that you may have about the study?

**I would like to verify your contact information. Is this your correct mailing address and telephone number?**

**Yes – great thank you!** *(move to next question)*

**No – obtain correct information and update spreadsheet.**

**We also have \_\_\_\_\_ (name) as a friend or family member who would know your whereabouts in case we have trouble contacting you. Is this still the correct phone number for \_\_\_\_\_ (name)?**

**Yes – go to close out**

**No – Can you give me another person who would know your whereabouts in case we have trouble contacting you? Please think of someone who would not mind if we called them for this information.**

***Close out:***

- ***Thank you again for your time today.*** A member of our team will be contacting you each month by mail or phone. If you would like to reach us before we talk again you can call us at the number listed on your DVD. If your phone number or address changes, or if you have any questions about the Living Well with Diabetes study, please call us at the same number. Thank you and have a wonderful day!

## General Health Program Participant Phone Call Script – Month 5

### *Voicemail leave message 1 time only:*

Hello, my name is \_\_\_\_\_, I am calling from the University of Alabama at Birmingham about the Living Well program. At your convenience, please call us at [contact]. Thank you and have a nice day.

Hello \_\_\_\_\_, my name is \_\_\_\_\_ calling from the University of Alabama at Birmingham about the Living Well research program. How are you today?

May I please speak with \_\_\_\_\_?

- [If not speaking] Is \_\_\_\_\_ available?
- [If no] When may I call back to speak with \_\_\_\_\_? Thank you for your time.  
[Document Date/Time to call back] \_\_\_\_\_
- **[If yes continue when they come on the line]** Hello \_\_\_\_\_, my name is \_\_\_\_\_ calling from the University of Alabama at Birmingham about the Living Well study. How are you today?

### **I am calling today to check in with you and remind you that your 2nd study visit and telephone interview are coming up in 1 month.**

Your 2nd telephone interview and your study visit are coming up in 1 month. Let me tell you a little about these visits. During the telephone interview, we will ask you some questions about you and your diabetes. At the in-person data collection visit, UAB staff will do a finger stick test to check your A1c number, which is your average blood sugar level, and your blood cholesterol. They will also measure your height, weight, blood pressure, and make a list of your medications.

- Remember, you will receive a \$20 VISA gift card for completing the inperson study visit.
- Would you like to schedule this visit and telephone interview today?
  - o if no: Okay, I will give you a in 2-3 weeks.
  - o If yes, schedule date and times: Great! We see you on \_\_\_\_\_ (date/time)!
- May I answer any questions that you may have about the study?

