### **Purpose of the Research**

---

We are asking you to take part in a research study. This research study will test if Peer Advisors can help patients with diabetes better care for his or her diabetes to improve blood sugar levels, blood pressure, and quality of life. Peer advisors come from the same community as participants and have been trained to help people with diabetes. This study will enroll 500 participants. 250 participants will work with a peer advisor for 6 months and 250 participants in the general education group will receive health education videos. Which program you receive will depend on a random assignment process.

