### *Close out:*

- *Thank you again for your time today.* We will talk to you on [date/time] to complete your telephone interview and on [date/time] to complete your 2nd in person study visit.
- *For your in person study visit,* We ask that you do not to not drink any caffeine (from coffee, tea, or soda), should not eat or do any heavy physical activity, smoke, ingest alcohol for 30 minutes prior to the in person data collection visit. *Please wear a loose fitting shirt to the study visit.*
- Thank you and have a wonderful day!

## Living Well Program Participant Phone Call Script – Month 2

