### **I am calling today to check in with you and remind you that your 2nd study visit and telephone interview are coming up in 1 month.**

- Have you spoken to your peer advisor? How many times in the past 4 weeks have you spoken to your peer (NAME HERE)
- Your 2nd telephone interview and your study visit are coming up in 1 month. Let me tell you a little about these visits. During the telephone interview, we will ask you some questions about you and your diabetes. At the in-person data collection visit, UAB staff will do a finger stick test to check your A1c number, which is your average blood sugar level, and your blood cholesterol. They will also measure your height, weight, blood pressure, and make a list of your medications.
- Remember, you will receive a \$20 VISA gift card for completing the inperson study visit.
- Would you like to schedule this visit and telephone interview today?
  - o if no: Okay, I will give you a in 2-3 weeks.
  - o If yes, schedule date and times: Great! We will call you on the phone and send you a reminder in your mail before the visits as a reminder.
- May I answer any questions that you may have about the study?

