### **I would like to verify your contact information. Is this your correct mailing address and telephone number?**

**Yes – great thank you!** *(move to next question)*

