**No – obtain correct information and update spreadsheet.**

### **We also have \_\_\_\_\_ (name) as a friend or family member who would know your whereabouts in case we have trouble contacting you. Is this still the correct phone number for \_\_\_\_\_ (name)?**

**Yes – go to close out**

**No – Can you give me another person who would know your whereabouts in case we have trouble contacting you? Please think of someone who would not mind if we called them for this information.**

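### The month-5 retention calls differ by arm: only the peer script re-checks contact details and promises reminders, and only the control script gives the pre-visit instructions

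*Combined protocol and SAP*

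**What the plan says.** Appendix G, Retention Scripts, holds five staff call scripts: General Health Program (control) at months 1, 3 and 5, and Living Well Program (peer arm) at months 2 and 5. The outcome visit falls at 6 months; participants are told at baseline that "another data collection will take place in 6 months".

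The two month-5 scripts open almost alike. Both announce the second interview and visit, describe them, mention the gift card and offer to book. If the visit is not booked, both provide for another call in 2 to 3 weeks. They then part:

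- **Control, month 5.** A participant who books hears "If yes, schedule date and times: Great! We see you on" and the date. The close-out confirms the appointments ("We will talk to you on [date/time] to complete your telephone interview", and likewise the visit), gives preparation instructions and ends. It does not ask about address, telephone number or tracing contact.
- **Peer arm, month 5.** A participant who books hears "We will call you on the phone and send you a reminder in your mail before the visits as a reminder". The script continues "I would like to verify your contact information. Is this your correct mailing address and telephone number", then checks the person held on file "as a friend or family member who would know your whereabouts in case we have trouble contacting you". If that person's details no longer hold, it asks "Can you give me another person who would know your whereabouts in case we have trouble contacting you". The close-out confirms the appointments and gives no preparation instructions.

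**The concern.** Contact checks, reminders and visit preparation are trial conduct, not intervention content. The text available gives no reason for them to differ by arm, and the check that protects the outcome most is the last one before it.

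The follow-up described to participants is one repeat interview and one repeat visit. The visit may take place at home, so the address can matter for collecting A1c and blood pressure as well as for mail. The tracing contact exists for people who can no longer be reached. If effort on these items differs by arm just before the outcome, completeness of follow-up can differ by arm too.

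The preparation text raises a separate, smaller issue. The Biometric Protocol (Appendix F, Blood Pressure, Participant Preparation) asks participants to avoid caffeine, food, heavy activity, smoking and alcohol for 30 minutes before the reading. A prompt given to one arm only could make preparation for that measurement unequal.

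**Working it through.** No stated figure is at issue. The check sets the five scripts side by side and dates the last contact check.

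| Script | Address and telephone check | Tracing-contact check | Reminder promised on booking | Visit preparation |
|---|---|---|---|---|
| Control, month 1 | yes | yes | no booking step | no |
| Peer arm, month 2 | yes | yes | no booking step | no |
| Control, month 3 | yes | yes | no booking step | no |
| Control, month 5 | **no** | **no** | **no** | yes |
| Peer arm, month 5 | yes | yes | yes, call and mail | **no** |

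1. Number of scripted checks: control 2 (months 1 and 3), peer arm 2 (months 2 and 5). The arms are equal in number and differ in timing.
2. Age of the last scripted check at the outcome visit = 6 months minus the month of that check.
   - Control: 6 − 3 = 3 months.
   - Peer arm: 6 − 5 = 1 month.
   - Gap: 3 − 1 = 2 months.
3. Which details the gap affects. A control who answers in month 5 has shown that the number works that day. What stays unconfirmed is mainly the mailing address and the tracing contact.
4. With the verification block added to the control script, both arms stand at 6 − 5 = 1 month.

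These ages assume that the calls are made on schedule and answered. The gap concerns two arms of planned equal size: "250 participants will work with a peer advisor for 6 months and 250 participants in the general education group will receive health education videos".

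Other contact near the outcome also differs. The peer arm has peer sessions at weeks 20 and 24, with up to eight logged call attempts and notice to the community coordinator if all numbers are disconnected. That belongs to the intervention and cannot be equalised. It does leave the month-5 staff call as the last scripted live contact for controls before follow-up is arranged.

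**The case against.** The case that this matters little is fairly strong, and most of it stands.

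- **Contact is not lower for controls in every respect.** They have three scripted staff calls against two. Both arms are told to expect monthly contact by mail or telephone, and both are asked to report changes of number or address.
- **A reader might infer that controls receive no reminder.** The documents do not support that. The retention postcards in Appendix G include two announcing the 6-month visit and an appointment card for the telephone interview. The text available shows no limit to the peer arm, and these cards follow a General Health video card. Nor does the peer script promise reminders to everyone, since the sentence is read only to those who book.
- **The 6-month interview may close the gap.** The baseline Telephone Interview (Appendix E) ends by repeating the preparation instructions, promising a mailed card and a call the day before the visit, and verifying contact details. If the 6-month interview follows that form and precedes the visit, both arms get all of this. The 6-month script is not shown, and the first part of the document, also not shown, may contain common retention rules.
- **The block is read only to people who were reached.** Someone who cannot be reached in month 5 is not verified in either arm. Those affected by the omission have just answered the telephone and can book on that call. People planning to leave the county within 6 months were also screened out.

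Two things remain. Mailed reminders rely on an address last checked in controls at month 3, and a check at the 6-month interview helps only those who are reached for it. The written scripts still differ with no stated reason.

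**Conclusion.** The month-5 scripts are unequal in both directions. Controls lack the contact and tracing check and the reminder sentence; the peer arm lacks the preparation text. The firm size is a gap of about 2 months in the age of the last scripted contact check, 3 months against 1.

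An effect on loss to follow-up is possible and probably small. A reader might go further and count how many controls would be lost, by applying a monthly rate of changed details to the gap. The documents give no such rate, and the product would count out-of-date details among people just reached, not losses. A reader might also infer a bias that analysis could not repair. That does not follow: unequal wording need not produce unequal missingness, unequal missingness need not bias the comparison, and the handling of missing data is not in the part available.

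The effect of the missing preparation text on peer-arm blood pressure cannot be sized either. The measurement procedure itself requires a 5-minute rest and at least 30 minutes since caffeine, which limits it.

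This is a low-cost correction worth making. It does not show that the comparison is biased.

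**What to change.** Use one common block in both month-5 scripts:

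- In the General Health script, between the scheduling step and the close-out, insert the address and telephone question and the tracing-contact questions from the Living Well month-5 script. Add that script's reminder sentence to the branch for participants who book.
- In the Living Well close-out, insert the visit-preparation text from the General Health close-out, including the request for a loose shirt.
- Leave only the program-specific question, on conversations with the peer advisor, different between arms.

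Both edits are needed. Changing the control script alone would leave the preparation text unequal. It would also help to label the reminder cards in Appendix G with the arm or arms that receive them, and to report completion of the 6-month interview and visit by arm.

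The cost is a few lines of existing text in two scripts and about one minute per call.
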